## 7 PROTOCOL AMENDMENTS

Modification of the protocol is prohibited without prior written agreement in the form of a protocol amendment. All amendments will be created by the Sponsor and must be approved by the IEC/IRB prior to implementation except when required to mitigate immediate safety risks or when the changes involve only logistical or administrative revisions.

## 8 SUBJECT POPULATION

The study population includes approximately 35 subjects to be enrolled at approximately 2 sites. To participate in the study, a subject must be 18 years or older and a successful wearer of spherical soft contact lenses in a daily wear modality during the past 3 months for a minimum of 5 days per week and 8 hours per day. The complete inclusion and exclusion criteria are presented in Section 1. The expected duration of subject participation in the study is 3 to 9 days (4 visits on 2 study days).

## 9 TREATMENTS ADMINISTERED

Upon entry into the study, subjects will be assigned numbers in the appropriate numerical sequence by designated staff at each investigational site. Qualifying subjects will be randomized in a 1:1:1:1 manner to one of the following lens sequences, where each pair consists of a test and a control lens:

- Test 1 (OD)/ Control (OS) → Control (OD)/ Test 2 (OS)
- Test 2 (OD)/ Control (OS) → Control (OD)/ Test 1 (OS)
- Control (OD)/ Test 1 (OS) → Test 2 (OD)/ Control (OS)
- Control (OD)/ Test 2 (OS) → Test 1 (OD)/ Control (OS)

Throughout the study, the Investigator will be responsible for the accounting of all study contact lenses and will ensure that the study contact lenses are not used in any unauthorized manner.

### 9.1 Identity of Study Treatments

Test Lenses: Monthly contact lens with Coating 1 [REDACTED] pre-cycled with OPTI-FREE RepleniSH multi-purpose disinfection solution (Test 1)

Monthly contact lens with Coating 2 [REDACTED] pre-cycled with OPTI-FREE RepleniSH multi-purpose disinfection solution (Test 2)

Control Lenses: PureVision contact lenses pre-cycled with OPTI-FREE RepleniSH multi-purpose disinfection solution (Control)

Both test lenses [REDACTED] will be provided in blister foil packaging with investigational labeling, which includes at a minimum the following: power, base curve, diameter, lot number, expiration date, and investigational use statement. Prior to commencement of the study, the Investigator will receive sets of [REDACTED] and [REDACTED] [REDACTED] lenses for pre-cycling, fitting and dispensing.

PureVision is a marketed product. Lenses for the study will be provided in original blister foil packaging with commercial labeling, which includes at a minimum: brand name, material, manufacturer, power, base curve, diameter, lot number and expiration date. Prior to commencement of the study, the Investigator will receive a set of PureVision lenses for pre-cycling, fitting and dispensing.

## 9.2 Usage

This study is a contralateral crossover study and qualifying subjects will wear 2 pairs of study lenses according to the randomized lens sequence assignment. All lenses will be pre-cycled in OptiFree RepleniSH multi-purpose disinfection solution. [REDACTED]

[REDACTED] Each pair of study lenses (one test and one control) will be dispensed to the subject for contralateral wear, to be worn for 2 hours (-15 min / +1 hour) and then collected from the subject. Wear time is defined as time from lens insertion to lens removal. Test and control lenses will only be available in  $0.00\text{ D} \pm 0.50\text{ D}$ , so while wearing study lenses subjects will wear habitual spectacles as needed for vision correction. Subjects will be instructed not to use topical ocular medications or lubricating drops during study lens wear.

Subjects will be instructed not to wear any contact lenses for a washout period comprising the day prior to and day of study visits. Subjects may wear their habitual contact lenses between visit days except for during the washout period.

Subjects will use and care for the study lenses as instructed by the Investigator or delegate, [REDACTED]

## 9.3 Accountability Procedures

Upon receipt of the investigational product (test and control lenses), the Investigator or delegate will conduct an inventory. Designated study staff will provide the study lenses to the subjects in accordance with their sequentially assigned subject numbers and the randomization schedule. During the study, the Investigator must maintain records of study lens dispensation and collection for each subject. This record must be made available to the study monitor for the purposes of verifying the accounting of clinical supplies. Any discrepancies and/or deficiencies between the observed disposition and the written account must be recorded along with an explanation. At the conclusion of the study, the Investigator will be responsible for returning all lidding foils, used and unused study lenses, and used and unused study supplies, unless otherwise instructed by the Sponsor.

## 9.4 Subject Confidentiality and Methods Used to Minimize Bias

The Investigator must ensure that the subject's anonymity is maintained throughout the course of the study. In particular, the Investigator must keep an enrollment log with confidential identifying information that corresponds to the subject numbers and initials of each study participant. At the end of the clinical study, the Sponsor will collect a copy of the enrollment log without any identifying subject information. All documents submitted to the

Sponsor will identify the subjects exclusively by number and demographic information. No other personally identifying information should be transmitted to the Sponsor.

The intent of masking is to limit the occurrence of conscious and unconscious bias in the conduct and interpretation of the clinical study. Bias could arise from the influence that the knowledge of a specific treatment assignment may have on the recruitment and allocation of subjects, their subsequent care, the assessment of end points, the handling of withdrawals, and so on. The essential aim of masking, therefore, is to prevent identification of the treatments by the Investigator, subject, and others associated with the conduct of the study until all such opportunities for bias have passed.

This study is double-masked, with subjects randomized to use Test 1, Test 2, and Control in the assigned eyes and lens sequence. The Investigators, Investigators' staff (other than unmasked study coordinators), subjects, and Sponsor personnel (other than the Lead Clinical Site Manager, site monitors and unmasked data managers) involved in reporting, obtaining, and/or reviewing the clinical evaluations will not be aware of the specific treatment being administered. This level of masking will be maintained throughout the conduct of the study.

Subjects will be assigned lens sequence in numerical order; the randomization schedule will be blocked to ensure a balance of study lens sequence allocations within investigational sites. The randomization scheme will be generated and maintained by the Sponsor. Individual subjects may be unmasked only once all study data have been verified and validated and the database has been locked. In the event of a medical emergency where the knowledge of subject treatment is required, an individual Investigator will have the ability to unmask the lens sequence assignment for a specific subject.

## 10 STUDY PROCEDURES

### 10.1 Outline of Study

This double-masked, randomized, contralateral, crossover, active controlled study will evaluate 2 surface coating candidates in subjects at least 18 years of age who are experienced wearers of spherical soft contact lenses and qualified according to all inclusion and exclusion criteria. Approximately 35 subjects will be enrolled and qualifying subjects will be randomized to wear 2 pair of study lenses and will attend 4 visits occurring on 2 different study days (2 visits per day, approximately 2 hours of wear time per lens pair). Visits 1 and 2 (Pair 1 dispense and follow-up) occur on the same study day and 2 to 8 days later Visits 3 and 4 (Pair 2 dispense and follow-up) occur. Subjects must not wear contact lenses for a washout period that includes the day of and day prior to study visits.

### 10.2 Visits and Examinations

Study lenses must be pre-cycled with OPTI-FREE RepleniSH multi-purpose disinfection solution prior to dispensing. [REDACTED]

#### 10.2.1 Visit 1 (Day 1) – Screening/Baseline/Pair 1 Dispense

1	Explain the purpose and nature of the study, and have the subject read, sign, and date the IRB-approved informed consent document (ICF). Additionally, have the individual obtaining consent from the subject and a witness, if applicable, sign and date the informed consent document. Provide a photocopy of the signed document to the subject and place the original signed document in the subject's chart. After signing the ICF, a subject will be assigned a subject number by the EDC system. A signed ICF defines the point of enrollment.
2	Confirm the subject has not worn contact lenses on the day of and the day prior to the visit. If lenses have been worn, reschedule Visit 1 to allow for the washout period.
3	Obtain demographic information and medical history, including information on all medications used within the past 30 days. Include herbal therapies, vitamins, and all over-the-counter as well as prescription medications. [REDACTED]

4	
Perform Snellen VA with habitual spectacles.
 

• OD, OS, OU, distance only

 
[REDACTED]
 
Note: Distance VA with habitual spectacles must be 20/40 OU or better for the subject to qualify for the study.

5	Perform a manifest refraction.
6	
Perform Snellen BCVA with manifest refraction.
 

• OD, OS, distance only

 
Note: Distance BCVA must be 20/25 or better in each eye for the subject to qualify for the study.

7	
Perform slit-lamp biomicroscopy (without contact lenses) to evaluate the following:
 

• Limbal hyperemia

• Bulbar hyperemia

• Corneal staining – 5 regions (type, area)

• Conjunctival staining

• Corneal vascularization

• Corneal epithelial edema

• Corneal stromal edema

• Conjunctival compression/indention

• Chemosis

• Palpebral conjunctival observations

• Corneal infiltrates

• Other findings

8	
Review inclusion/exclusion criteria to determine if subject qualifies for participation in the study.
 

• If subject qualifies, continue to randomization (step 9)

• If a subject qualifies according to all criteria except for unacceptable corneal staining, they will be permitted to return within 7 days to be reassessed. The Investigator will determine if it is permissible for the subject to use preservative-free lubricating drops prior to returning for reassessment. The use of preservative-free eye drops should not be considered a treatment, but rather a palliative measure to reduce corneal staining, and as such should not trigger an adverse event. If upon reassessment corneal staining remains unacceptable, exit subject from study as a screen failure.

• If a subject does not qualify according to any criterion other than unacceptable corneal staining, exit subject from study as a screen failure.

9	
Based on the randomized lens sequence assignment, have the subject insert Pair 1 study lenses, being careful to maintain the correct OD and OS lens assignments.
 

• Keep all lidding foils of lenses used during lens fit process for study lens accountability.

• Follow procedures to maintain masking.

13	Assess and record any AEs and device deficiencies reported or observed during the study visit.  Note: AEs and device deficiencies must be recorded for all enrolled subjects from the time of signature of informed consent including those that screen fail.
14	Dispense study lenses for approximately 2 hours of wear and instruct the subject to refrain from using any topical ocular medications or eye drops until they remove lenses at Visit 2.
15	Schedule Visit 2 to take place 2 hours (-15 min/+1 hour) after Visit 1.

### 10.2.2 Visit 2 [Day 1, 2 hours (-15 min/+1 hour)] – Pair 1 Follow-up

1	Obtain information on any changes in medical health and/or the use of concomitant medications.
2	Record any adverse events or device deficiencies that are observed or reported, including those associated with changes in concomitant medication dosing.
3	Review subject compliance with lens wear and adjunct product usage.
4	Have subject remove study lenses.
5	

8	
Perform slit-lamp biomicroscopy (without contact lenses) to evaluate the following:
 
 
• Limbal hyperemia
 
• Bulbar hyperemia
 
• Corneal staining – 5 regions (type, area)
 
• Conjunctival staining
 
• Corneal vascularization
 
• Corneal epithelial edema
 
• Corneal stromal edema
 
• Conjunctival compression/indention
 
• Chemosis
 
• Palpebral conjunctival observations
 
• Corneal infiltrates
 
• Other findings
 

9	
Perform Snellen VA with habitual spectacles.
 
 
• OD, OS, OU as needed, distance only
 
 
Note: If this VA with spectacle correction shows a decrease of 2 lines or more versus Visit 1 baseline VA with spectacle correction, then BCVA with MR is required to confirm a potential loss in VA for AE reporting requirements (see Section 12).

10	
Schedule Visit 3 to take place 2 to 8 days after Visit 2. Remind subjects not to wear contact lenses on the day of or prior to Visit 3.

### 10.2.3 Visit 3 (+ 2 to 8 Days) –Baseline/Pair 2 Dispense

1	Obtain information on any changes in medical health and/or the use of concomitant medications.
2	Record any adverse events or device deficiencies that are observed or reported, including those associated with changes in concomitant medication dosing.
3	Review subject compliance with washout period. If lenses have been worn, reschedule Visit 3 to allow for the washout period.

4	
Perform Snellen VA with habitual spectacles.
 

• OD, OS, distance only

 
Note: If this VA with spectacle correction shows a decrease of 2 lines or more versus Visit 1 baseline VA with spectacle correction, then BCVA with MR is required to confirm a potential loss in VA for AE reporting requirements (see Section 12).

5	
Perform slit-lamp biomicroscopy (without contact lenses) to evaluate the following:
 

• Limbal hyperemia

• Bulbar hyperemia

• Corneal staining – 5 regions (type, area)

• Conjunctival staining

• Corneal vascularization

• Corneal epithelial edema

• Corneal stromal edema

• Conjunctival compression/indentation

• Chemosis

• Palpebral conjunctival observations

• Corneal infiltrates

• Other findings

6	
Review exclusion criteria (#5) related to corneal staining.
 

• If subject fulfills criteria, go to step 7.

• If subject shows unacceptable corneal staining, they will be permitted to return within 7 days to be reassessed. The Investigator will determine if it is permissible for the subject to use preservative-free lubricating drops prior to returning for reassessment. The use of preservative-free eye drops should not be considered a treatment, but rather a palliative measure to reduce corneal staining, and as such should not trigger an adverse event. If upon reassessment corneal staining remains unacceptable, discontinue the subject from the trial.

7	
Based on the randomized lens sequence assignment, have the subject insert the Pair 2 study lenses to be evaluated, being careful to maintain the correct OD and OS lens assignments.
 
Note: Keep all lidding foils of lenses used during lens fit process for study lens accountability.

11	
Dispense study lenses for approximately 2 hours of wear and instruct the subject to refrain from using any topical ocular medications or eye drops until they remove lenses at Visit 4.

12	
Schedule Visit 4 to take place 2 hours (-15 min/+1 hour) after Visit 3.

#### 10.2.4 Visit 4 [same day as Visit 3, 2 hours (-15 min/+1 hour)] – Pair 2 Follow-up / Exit

1	
Obtain information on any changes in medical health and/or the use of concomitant medications.

2	
Record any adverse events or device deficiencies that are observed or reported, including those associated with changes in concomitant medication dosing.

3	Review subject compliance with lens wear and adjunct product usage.
6	Have subject remove study lenses.
8	Perform slit-lamp biomicroscopy (without contact lenses) to evaluate the following: 

• Limbal hyperemia

• Bulbar hyperemia

• Corneal staining – 5 regions (type, area)

• Conjunctival staining

• Corneal vascularization

• Corneal epithelial edema

• Corneal stromal edema

• Conjunctival compression/indention

• Chemosis

• Palpebral conjunctival observations

• Corneal infiltrates

• Other findings

9	Perform Snellen VA with habitual spectacles. 

• OD, OS, distance only

 
Note: If this VA with spectacle correction shows a decrease of 2 lines or more versus Visit 1 baseline VA with spectacle correction, then BCVA with MR is required to confirm a potential loss in VA for AE reporting requirements (see Section 12).

10	Exit the subject from the study.

## 10.3 Unscheduled Visits

Any visit that occurs between the regularly scheduled visits must be documented in the Unscheduled Visit pages of the Case Report Form (CRF). During all unscheduled visits, the following procedures should be conducted: update medical history and concomitant medications, VA with spectacle correction [REDACTED] biomicroscopy [REDACTED] [REDACTED], assess and collect any AEs or device deficiencies.

If the subject is discontinuing at the unscheduled visit, all exit procedures must be completed (as possible) and the CRFs for Exit should be completed rather than the CRFs for an Unscheduled Visit.

## 10.4 Discontinued Subjects

Discontinued subjects are those who withdraw or are withdrawn from the study after signing the informed consent, including screen failures. Subjects may discontinue from the study at any time for any reason. Subjects may also be discontinued from the study at any time if, in the opinion of the Investigator, their continued participation poses a risk to their health. Discontinued subjects will not be replaced (ie, their subject numbers will not be re-assigned/re-used).

Should a subject exhibit any clinically relevant signs, symptoms, or other clinical observations that possibly could be associated with suspected sensitivity or intolerance to one of the study treatments, the Investigator must document those observations on an AE Form.

Any subject who exits early from the study must undergo all procedures outlined at Visit 4, as applicable. Additionally, the Exit Form must be completed and the reason for discontinuation must be identified.

Finally, to ensure the safety of all subjects who discontinue early, Investigators should assess each subject and, if necessary, advise them of any therapies and/or medical procedures that might be needed to maintain their health.

## 10.5 Clinical Study Termination

If the clinical study is prematurely terminated or suspended, the Sponsor will inform the Investigator and the regulatory authorities of the termination/ suspension and the reason(s) for the termination/suspension. The Investigator should promptly notify the IEC/IRB of the termination or suspension and of the reasons. The Sponsor reserves the right to close the

investigational site or terminate the study in its entirety at any time, for reasonable cause.

Reasons for the closure of an investigational site or termination of a study may include:

- Successful completion of the study
- The study's enrollment goals are met
- The Investigator fails to comply with the protocol or GCP guidelines
- Safety concerns
- Sufficient data suggesting lack of efficacy
- Inadequate recruitment of subjects by the Investigator

The Investigator also may terminate the study at his/her site for reasonable cause. If the Sponsor terminates the study for safety reasons, it will immediately notify the Investigator(s) by telephone and subsequently will provide written confirmation of and instructions for study termination.

## **10.6 Enrollment Stopping Criteria**

Prior experience with first time exposure of new contact lens materials indicates the following potential findings:

- Severe, persistent burning/stinging – onset within seconds following lens insertion
- Severe lens awareness/discomfort or blurred vision with IP due to very poor surface wetting – onset: minutes to hours following lens insertion.

In order to protect subject safety, the following stopping criteria are established for this clinical study:

IF approximately 20% of subjects (7 subjects) experience findings described above following contact lens wear and the event(s) are deemed to be related to study lens wear, THEN enrollment of additional subjects will be stopped across sites and a root-cause analysis of the events will be conducted.

The Investigator must report the above findings to the Sponsor immediately by telephone (refer to Alcon contact list [REDACTED]). If the Sponsor stops enrollment in the study due to the above criteria, it will immediately notify the Investigator(s) by telephone. The Investigator should promptly notify the IEC/IRB of the implementation of stopping rules and reason(s).

Enrollment may be resumed upon determination of causality by the Sponsor Medical Expert or an independent medical expert and applicable IRB requirements completed.

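### At 7 lens-related severe cases, Section 10.6 stops enrollment but requires no hold on lenses for subjects already enrolled, who are still due a first exposure to the other untested coating

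*Protocol*

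**What the plan says.** Protocol Section 10.6 starts from experience with new materials: "Prior experience with first time exposure of new contact lens materials indicates the following potential findings". It lists severe persistent burning or stinging, starting within seconds of insertion, and severe awareness, discomfort or blurred vision from poor wetting, starting within minutes to hours. Its stated purpose is subject safety. The trigger is "IF approximately 20% of subjects (7 subjects) experience findings described above following contact lens wear", with the events judged related to study lens wear. The action is "THEN enrollment of additional subjects will be stopped across sites and a root-cause analysis of the events will be conducted".

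Three notification duties go with the rule. The Investigator must telephone the findings to the Sponsor immediately. The Sponsor must telephone Investigators if it stops enrollment. The Investigator should promptly tell the IEC/IRB. The release sentence is again about enrollment: "Enrollment may be resumed upon determination of causality by the Sponsor Medical Expert or an independent medical expert", once IRB requirements are met.

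For dosing, Section 9 says "Qualifying subjects will be randomized in a 1:1:1:1 manner to one of the following lens sequences", each sequence having two pairs of one test and one control lens. Section 10.2.1 defines enrollment as the signed consent form. At Visit 3 (Section 10.2.3), step 3 checks washout, step 6 is "Review exclusion criteria (#5) related to corneal staining", and step 7 is to "have the subject insert the Pair 2 study lenses to be evaluated". Section 5.2 says that the coatings have not yet been evaluated in clinical trials.

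**The concern.** The rule is written for first exposure to a new material. In this crossover each subject has two such exposures, and the rule acts only on people who have not yet consented. If one coating is at fault, subjects who wore the other one first would still be given the suspect coating while its cause is being investigated. A subject who tolerated Pair 1 gives no information about the coating in Pair 2, and the Investigator is masked to which coating that is. Section 5.3 states that subjects have no intended clinical benefit to set against the exposure.

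Timing sharpens the point. If the true rate is near the 20% that the rule names, the seventh case comes late in enrollment. By then, Pair 2 is the main exposure that can still be prevented.

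**Working it through.** **1. The plan's own figure.** 20% of the 35 planned subjects is 0.20 × 35 = 7.0, so the trigger reproduces. Against the 32 required completers it would be 7/32 = 21.9%.

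**2. What Pair 2 contains (Section 9).**

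| Sequence | Coating in Pair 1 | Coating in Pair 2 |
|---|---|---|
| 1 | Test 1 | Test 2 |
| 2 | Test 2 | Test 1 |
| 3 | Test 1 | Test 2 |
| 4 | Test 2 | Test 1 |

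In 4 of 4 sequences Pair 2 is the first exposure to the other coating.

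**3. Who falls outside the stop.** Enrollment is consent. A subject between Visits 2 and 3 (2 to 8 days) is enrolled and due Pair 2. A consented subject sent home at Visit 1 for staining reassessment is also enrolled, and would receive Pair 1 if they then qualify. The stated checks before Pair 2 insertion are washout and staining. Visit 3 steps 8 to 10 are not visible in the public text, but they follow insertion.

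**4. How often the rule fires.** Let q be the share of subjects affected. With n exposed, P(fires) = P(X ≥ 7), X ~ Binomial(n, q).

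| q | n = 35 | n = 32 |
|---|---|---|
| 10% | 0.055 | 0.036 |
| 20% | 0.567 | 0.465 |
| 30% | 0.935 | 0.887 |
| 40% | 0.997 | 0.991 |

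The expected number of subjects needed for 7 cases is 7/q: 35, 23.3 and 17.5 at q = 20%, 30% and 40%.

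**5. Who is left when it fires.** The documents give no rates or pace, so these inputs are assumptions:
- One coating affects a share q of subjects; the other coating and the control affect none.
- Subjects are independent, and all 35 wear lenses.
- The offending coating comes first in half of the subjects (blocks of 4).
- Pace is 1, 2, 4 or 8 per day, and the gap is 2, 5 or 8 days.

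Each case is counted when the offending coating is worn. Means are over simulated trials in which the rule fires. At 4 per day and a 5-day gap:

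| | q = 20% | q = 30% | q = 40% |
|---|---|---|---|
| Enrolled, still due Pair 2 | 13.5 | 17.5 | 19.4 |
| Of these, due the offending coating | 6.5 | 8.5 | 9.5 |
| Expected affected (previous row × q) | 1.3 | 2.6 | 3.8 |
| Not yet enrolled, spared by the rule as written | 1.6 | 4.2 | 7.9 |

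Range over all paces and gaps:

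| | q = 20% | q = 30% | q = 40% |
|---|---|---|---|
| Still due Pair 2 | 2 to 16 | 2 to 23 | 2 to 27 |
| Due the offending coating | 0.7 to 8 | 0.7 to 11 | 0.7 to 13 |
| Expected affected | 0.1 to 1.6 | 0.2 to 3.4 | 0.3 to 5.3 |
| Probability that nobody is left to enroll | 0.11 to 0.94 | 0.035 to 0.76 | under 0.01 to 0.45 |

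The first row includes subjects already affected in Pair 1: about 2.0 of 13.5 at q = 20% and 4.3 of 19.4 at q = 40% (4 per day, 5 days). They are due the harmless coating, so the offending-coating and affected rows do not include them.

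**The case against.** The strongest reply is that the protocol does not leave sites uninformed or powerless. Telephone reporting is mandatory from the first case. Investigators are told at once when enrollment stops, and the IEC/IRB should be told promptly. The Investigator may withdraw a subject at risk (Section 10.4). The Sponsor may suspend or terminate the study, and the Investigator may terminate it at the site (Section 10.5). Section 7 allows urgent safety changes before IEC/IRB approval. Section 5.2 adds clinician supervision and lens removal on symptoms. A Manual of Procedures, not available here, may say how a stop is handled. All of this stands, and a hold could well follow in practice. But the visible text does not make one follow from the trigger: the powers are discretionary, and supervision and removal act only once the lens is on the eye.

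A reader might infer that lens wear would carry on with nobody alerted, that every consented subject awaiting reassessment will be dosed, or that lasting injury is in prospect. The documents support none of these. The notices are required or expected, a reassessed subject gets Pair 1 only after qualifying, and the listed findings are symptoms over about 2 hours of wear. Nor is the written stop useless: it spares both pairs for anyone not yet enrolled.

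The size is also fairly disputed. It rests on one assumed pattern and an unknown pace. The upper figure of 5.3 needs q = 40% with fast enrollment and a long gap. If only 32 of the 35 wear lenses, the rule fires less often.

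**Conclusion.** The gap is real and follows from the text alone: the trigger can be met and Section 10.6 followed exactly while enrolled subjects still receive a second clinically untested coating. It is a gap in what the pre-set rule requires, not proof that dosing would continue.

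The likely size is modest. In the central scenario about 1.3 to 3.8 subjects would have avoidable symptoms, and over all assumed scenarios 0.1 to 5.3. These figures are conditional on the rule firing, which at q = 20% has probability 0.567 with 35 exposed or 0.465 with 32. The change is worth making because it is cheap and serves the rule's stated purpose. Confidence is medium, since the numbers depend on assumed rates and pace, and operational documents were not seen.

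**What to change.** Keep the trigger at 7 and make these changes:

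1. In Section 10.6, state that at the trigger both enrollment and all dispensing of study lenses (Pair 1 and Pair 2) are held across sites until causality is determined. The hold covers both coatings because the one at fault is not yet known.
2. Make the resumption sentence cover dispensing as well as enrollment.
3. Before Visit 3 step 7, add a check that no Section 10.6 hold is in force.
4. Allow held subjects to have Visit 3 after day 8 once the hold is lifted. There is precedent: a subject with unacceptable staining at Visit 3 already may come back, as "they will be permitted to return within 7 days to be reassessed", which puts Pair 2 up to 8 + 7 = 15 days after Visit 2.

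The drafting cost is a few sentences, and the rule fires no more often than now. The real cost arises if it fires. About half of those held are due the harmless coating in this scenario, and a hold that is never lifted loses completers. At 4 per day and a 5-day gap, ignoring other dropout:

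| q | Completers, hold never lifted | Completers, current rule, enrollment not resumed |
|---|---|---|
| 20% | 35 − 13.5 − 1.6 = 19.9 | 35 − 1.6 = 33.4 |
| 30% | 35 − 17.5 − 4.2 = 13.3 | 35 − 4.2 = 30.8 |
| 40% | 35 − 19.4 − 7.9 = 7.7 | 35 − 7.9 = 27.1 |

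The requirement is 32. The right-hand column is generous, because it assumes that subjects already affected in Pair 1 all continue. Change 4 limits the loss whenever the hold is lifted.
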